3.8.3.3 Withdrawal of Consent

All subjects have the right to withdraw their consent from further participation in the trial at any time without prejudice. Subjects cannot withdraw consent for use of data already collected as part of the trial, but only for future participation. The investigator can also discontinue a subject's participation in the trial at any time if medically necessary. Unless the subject provides their written withdrawal of consent or there is other written documentation by the investigator confirming the subject's verbal intent to completely withdraw from the trial, subjects should be followed for all protocol-specified evaluations and assessments, if possible.

Complete withdrawal of consent requires a subject's refusal of all of the following methods of follow-up (these methods of follow-up will also be noted in the trial ICF):

- Participation in all follow-up procedures specified in the protocol (whether in-clinic, by telephone, or by an in-home visit).
- Participation in a subset of protocol-specified follow-up procedures (by a frequency schedule and method, as agreed by subject and staff).
- Contact of the subject by trial personnel, even if only by telephone, to assess current medical condition, and obtain necessary medical or laboratory reports relevant to the trial's objectives.

Protocol 031-201-00301

- Contact of alternative person(s) who have been designated in source records as being available to discuss the subject's medical condition, even if only by telephone, mail, or email (eg, family, spouse, partner, legal representative, friend, neighbor, or physician).
- Access to medical information from alternative sources (eg, hospital/clinic medical records, referring doctor's notes, public records, dialysis, transplantation or vital registries, social media sources).

Withdrawal of consent is a critical trial event and therefore should be approached with the same degree of importance and care as is used in initially obtaining informed consent. The reasons for a subject's intended withdrawal need to be completely understood, documented, and managed to protect the rights of the subject and the integrity of the trial. A subject may initially express their desire to discontinue Abilify MyCite administration, which is not equivalent to a complete withdrawal of consent for further participation (see [Section 3.8.3.1](#)). A subject may, however, indicate that further trial participation is creating a burden on their work or social schedule. Therefore, the investigator should follow the procedures outlined in [Section 3.8.3.2](#) to determine if the subject can continue participation in the trial if modifications to his/her treatment and/or schedule of assessments can be accommodated. Only subjects who withdraw their permission for all of the above degrees of follow-up are considered to have completely withdrawn their consent to participate in the trial.

3.9 Screen Failures

A screen failure subject is one from whom informed consent is obtained and is documented in writing (ie, subject signs an ICF), but who is not started on trial treatment. For the purposes of this trial, Abilify MyCite treatment begins with the first administration of Abilify MyCite on Day 1 of the prospective phase. Subjects who sign an eICF but who are not started on treatment are permitted to be re-screened. In the event that the subject is re-screened for trial participation, and the re-screening is not completed within the original screening window, a new eICF must be signed.

3.10 Definition of Completed Subjects

The treatment period is defined as the time period during which subjects are evaluated for primary and/or secondary objectives of the trial irrespective of whether or not the subject actually received all doses of Abilify MyCite. For the purposes of this trial, subjects who complete the Month 6/ET visit will be defined as treatment completers. Subjects who are

Protocol 031-201-00301

evaluated at the last scheduled visit during the treatment period will be defined as trial completers.

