3.3 Trial Population

The trial population will include male and female subjects, 18 to 65 years of age, inclusive, with a diagnosis of schizophrenia according to DSM-5 criteria. Subjects must have had at least 1 inpatient psychiatric hospitalization within 4 years (48 months) prior to screening. Subjects must have been prescribed oral antipsychotic treatment for at least 6 months or longer prior to screening. Approximately 493 subjects will be screened in order to enroll 320 subjects and complete 224 subjects.

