3.7.1.3.5 Month 6/Early Termination Visit

Month 6/ET (- 3/ + 2 days) will be an investigator visit for the subject. In addition, Month 6/ET visit evaluations are to be completed for any subject withdrawn from the trial at any time (for any reason other than full withdrawal of the consent). At the Month 6/ET visit, the following will be performed:

- Administer the suicidality assessment (C-SSRS Since Last Visit Version; [Section 3.7.3.5](#)).
- Perform vital signs assessment ([Section 3.7.3.3](#)).
- Monitor AEs, including device-related nonserious AEs ([Section 5](#)).
- Accountability of patches and Abilify MyCite product (aripiprazole tablet embedded with an IEM sensor) supplies performed for subjects remaining on Abilify MyCite treatment. Any treatment changes, including reason for the change, will be recorded in the eCRF.
- Review Abilify MyCite dashboard data every 2 weeks for subjects remaining on Abilify MyCite treatment.

Protocol 031-201-00301

- [REDACTED]
- [REDACTED]
- [REDACTED]
- [REDACTED]
- [REDACTED]
- [REDACTED]
- Healthcare utilization record evaluation ([Section 3.7.1.4](#)).
- [REDACTED]
- [REDACTED]
- [REDACTED]
- [REDACTED]

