3.8.3 Individual Subject Discontinuation

3.8.3.1 Treatment Discontinuation

After enrollment, a subject may stop Abilify MyCite treatment permanently for a variety of reasons. Treatment discontinuations may be initiated by a subject who is not satisfied with treatment or may become medically necessary due to AEs, device-related nonserious AEs, required treatment with a disallowed medication or therapy, or other issues, as determined by the investigator. For subjects who elect to discontinue early for any reason, the sponsor would like to follow the subject for the total trial duration to track healthcare utilization with and without use of Abilify MyCite.

By Day 14 of the trial, if it is the opinion of the investigator that it is not appropriate for a subject to continue using Abilify MyCite, then the subject may be discontinued from trial participation but will be followed on oral atypical antipsychotic medication through the Month 6/ET visit.

If any subject discontinues the trial early, every effort should be made to complete the Month 6/ET evaluations (see [Table 3.7-1](#)) at that visit. All subjects (completers and early withdrawals) will be contacted to monitor for safety events via telephone or investigator visit at 1 month (\pm 3 days) after the Month 6/ET visit.

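### Protocol 3.10 labels an early terminator who attends the Month 6/ET visit a treatment completer; this affects completion reporting and the SAP's undefined Completer Sample, but not the primary analysis

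*Protocol*

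**What the plan says.** Protocol 3.10 gives two labels. For the first, "subjects who complete the Month 6/ET visit will be defined as treatment completers". The second, trial completer, is kept for subjects evaluated at the last scheduled visit of the treatment period. The same section defines that period "irrespective of whether or not the subject actually received all doses of Abilify MyCite", so dosing does not restrict either label.

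The schedule of assessments (protocol Table 3.7-1) has a single column for Month 6 and ET. Protocol 3.7.1.3.5 says that "Month 6/ET visit evaluations are to be completed for any subject withdrawn from the trial at any time", with one exception: it applies "for any reason other than full withdrawal of the consent". Protocol 3.8.3.1 adds that on early discontinuation "every effort should be made to complete the Month 6/ET evaluations". It also provides that a subject judged unsuitable for Abilify MyCite by Day 14 "will be followed on oral atypical antipsychotic medication through the Month 6/ET visit".

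The same section speaks of two distinct groups: "All subjects (completers and early withdrawals) will be contacted".

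On numbers, protocol 3.3 says: "Approximately 493 subjects will be screened in order to enroll 320 subjects and complete 224 subjects". Protocol 7.1 makes clear that the 224 are subjects who complete 3 months of treatment.

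SAP 7.4.1.1 tests change-from-baseline variables, and reports the discontinuation rate, on both an Efficacy Sample and a Completer Sample. SAP 5.1.1 lists the Enrolled, Safety, ITT and mITT samples and contains no Completer Sample.

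**The concern.** A completer definition exists to separate subjects who finished from subjects who left. This one rests on a visit that both groups are meant to attend, so attendance cannot tell them apart. Leaving early and cooperating with the exit visit earns the same label as six months on Abilify MyCite.

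Two things are at stake. First, any completion figure reported under the treatment-completer label could include dropouts and so look better than it is. Second, the SAP's Completer Sample has no definition of its own. The Efficacy Sample named beside it is defined only in the protocol (section 7.2), so a programmer looking for the Completer Sample would plausibly turn to the protocol section on completed subjects. The sample could then contain early terminators, and a discontinuation rate calculated on it would have no clear meaning.

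**Working it through.** **1. Classify typical subjects under the current text.**

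| Subject | Treatment completer (3.10, literal) | Trial completer (3.10) |
|---|---|---|
| On Abilify MyCite to the scheduled Month 6 visit | Yes | Yes |
| Switched to standard of care at Month 3, attends scheduled Month 6 | Yes | Yes |
| Taken off by Day 14, followed to scheduled Month 6 | Yes | Yes |
| Leaves in Week 2, attends the ET visit | Yes | No, on the natural reading |
| Fully withdraws consent, dies or is lost, with no visit | No | No |

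The fourth row is the defect: an early withdrawal under 3.8.3.1 is a treatment completer under 3.10. The two labels also invert, since that subject completes treatment but not the trial. The second and third rows show that the treatment label does not require being on the treatment.

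**2. Check whether the definition reaches the primary analysis.** The criteria used there are:

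- Sample size (protocol 7.1; SAP 4): completion of 3 months of treatment.
- Interim triggers (protocol 7.4.4; SAP 9): 50% and 70% of subjects through the 3-month prospective period.
- Protocol efficacy set (7.2): the first 3 months of dosing completed.
- SAP mITT (5.1.1): at least 80% of study medication in the period, plus complete hospitalization data.
- SAP sensitivity analysis (7.1.3): mITT subjects with at least 75 days in study.

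A Week 2 leaver meets none of the dosing or duration criteria. The subject stopped at Day 14 but followed to Month 6 would pass 75 days on time alone. With 14 of 84 days, 14/84 = 16.7%, that subject fails the 80% medication condition and is outside the mITT.

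**3. Reproduce the plan's figures.** For the fixed-design McNemar calculation, d = 0.135 − 0.05 = 0.085 and s = 0.135 + 0.05 = 0.185 (protocol 7.1), with two-sided alpha 0.05 and 80% power:

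n = [z(0.975)·√s + z(0.80)·√(s − d²)]² / d² = 198.6, or 199 rounded up, against 200 stated. Power at n = 200 is 80.3%.

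No completer definition enters this formula. For retention, 224/320 = 70%, so 320 − 224 = 96 subjects (30%) are planned non-completers, and 224/(1 − 0.30) = 320.

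**4. Scale of the mislabelling.** The documents give no ET attendance rate. Let f be the assumed share of the 96 who attend. Apparent completion = (224 + 96f)/320.

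| f | Counted as completers | Apparent completion |
|---|---|---|
| 0% | 224 | 70% |
| 25% | 248 | 77.5% |
| 50% | 272 | 85% |
| 75% | 296 | 92.5% |
| 100% | 320 | 100% |

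The 224 is a 3-month count and the definition concerns Month 6/ET, so the table shows scale and is not a forecast.

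**The case against.** The strongest reply is that this is loose wording with no demonstrated consequence. Section 3.10 goes on to define trial completers by the last scheduled visit, which an unplanned ET visit is not. Section 3.8.3.1 shows that the authors meant to keep completers and withdrawals apart. The SAP tabulates study duration and reasons for discontinuation (6.1), lists discontinued subjects with reasons (Appendix 2) and plots time to discontinuation (7.4.1.1), so early terminators will be visible as such. Exposure is summarized for Month 1-3 completers (8.2.1). Nothing says that the Completer Sample takes its meaning from protocol 3.10.

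Much of this stands. Those outputs limit the damage, and the intent is reasonably clear. But the written rule gives the opposite answer to the intent, and the trial-completer label does not repair the treatment-completer label. The missing Completer Sample definition is an SAP omission in its own right, and it is also what leaves protocol 3.10 available as the fallback.

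A reader might also infer that the sample size and interim looks are contaminated, because the re-estimation tables (protocol Table 7.4.4-1, SAP Table 9-1) are headed in completers and the synopsis speaks of 224 completed subjects. The documents do not support that: the governing text specifies 3-month completion each time. Nor does every withdrawn subject become a completer. Full withdrawal of consent is exempt, section 3.8.3.1 asks only for every effort, and only those who complete the visit are counted.

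**Conclusion.** The point holds as a misclassification of completion status. Protocol 3.10, taken with 3.7.1.3.5 and 3.8.3.1, labels early terminators who attend the ET visit as treatment completers and contradicts the protocol's own separation of the two groups. Its reach is completion and disposition reporting and the SAP 7.4.1.1 Completer Sample analyses. The latter are affected only if that sample is read through protocol 3.10, which the SAP neither states nor rules out.

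No primary estimate, test, power figure, sample size or interim decision changes. It would be tempting to conclude that the trial would report 100% completion instead of 70%. That requires all 96 planned non-completers to attend the ET visit, and it fails once a single subject fully withdraws consent, dies or is lost to follow-up. The supportable statement is a range under assumed attendance, 77.5% at one quarter rising towards the 100% bound. This is a minor point, worth correcting because the correction is cheap.

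**What to change.** In protocol 3.10:

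- Define the 6-month treatment completer as a subject who attended the scheduled Month 6 visit while still on Abilify MyCite.
- Report subjects switched to standard of care at Month 3 who attend the scheduled Month 6 visit as trial completers only.
- State that an ET visit does not count as completion under either label.

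In the SAP:

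- Add an explicit Completer Sample to section 5.1.1.
- For 3-month completion, use the rule already in SAP 7.1.3 (at least 75 days in study) and do not add a competing definition. SAP 7.1.3 applies that rule within the mITT, so say whether the 80% medication condition goes with it. Without that condition, a subject stopped at Day 14 but followed onwards would qualify on time alone.

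These are analysis labels; no visit, treatment or follow-up procedure changes. The cost is a few sentences and a possibly lower reported completion rate.

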3.11 Definition of Subjects Lost to Follow-up

Subjects who cannot be contacted on or before the last scheduled trial visit during the treatment period and who do not have a known reason for discontinuation (eg, withdrew consent or AE) will be classified as “lost to follow-up” as the reason for discontinuation.

The site will make 3 documented attempts to contact the subject by telephone and in the event the site is unable to reach the subject by telephone, the site will attempt to contact the subject via certified mail or an alternative similar method, where appropriate, before assigning a “lost to follow-up” status.

3.12 Subject Compliance

Subjects will be required to have at least 3 months of Abilify MyCite medication. Noncompliant subjects will be followed throughout the trial period and analysis will be performed as described in [Section 7.4](#). Discontinuation of noncompliant subjects is at the discretion of the investigator.

3.13 Protocol Deviations

In the event of a significant deviation from the protocol due to an emergency, accident, or mistake (eg, violation of informed consent process, Abilify MyCite dispensing or subject dosing error, treatment assignment error, subject enrolled in violation of eligibility criteria or concomitant medication criteria), the investigator or designee will contact the sponsor at the earliest possible time by telephone. The investigator and sponsor will come as quickly as possible to a joint decision regarding the subject’s continuation in the trial. This decision will be documented by the investigator and the sponsor and reviewed by the site monitor.

4 Restrictions

4.1 Prohibited Medications

The investigator may continue subjects on their stable/current mood stabilizer(s) or antidepressant dose (must be stable for at least 14-days prior to Abilify MyCite) to maintain clinical stability of the subjects during the trial. Other oral non-aripiprazole antipsychotic medications may be allowed if approved by the medical monitor and sponsor; however, clozapine will not be allowed. Nonoral formulations of these antipsychotic medications are also not allowed. The use of varenicline beyond the

Protocol 031-201-00301

screening visit is not allowed. If a subject is receiving varenicline at the screening visit, attempts should be made to discontinue the medication, if clinically feasible, to allow potential subjects to enter the trial.

Subjects must stop all other prohibited concomitant medications prior to administration of Abilify MyCite and for the duration of the trial.

Subjects must wash out from the following prohibited concomitant medications/therapies for the time periods specified:

- Use of approved long-acting antipsychotics within 6 months prior to signing the ICF.

Inhibitors and inducers of cytochrome P450 (CYP)3A4 and inhibitors of CYP2D6 isozymes are not allowed within 14 days (with the exception of fluoxetine which needs to be discontinued at least 28 days prior) prior to administration of Abilify MyCite and for the duration of the trial, since these are the pathways in which aripiprazole is metabolized.

An example list of CYP3A4 and CYP2D6 inhibitors and CYP3A4 inducers prohibited during the trial is provided in [Table 4.1-1](#).

Table 4.1-1 Example List of CYP3A4 and CYP2D6 Inhibitors and CYP3A4 Inducers Prohibited During the Trial	
CYP3A4 Inhibitors	
Amiodarone	Fluvoxamine
Amprenavir	Indinavir
Aprepitant	Itraconazole
Chloramphenicol	Ketoconazole
Cimetidine	Nefazodone
Clarithromycin	Nelfinavir
Clotrimazole (if used orally)	Quinupristin/Dalfopristin
Delavirdine	Ritonavir
Diltiazem	Saquinavir
Erythromycin	Troleandomycin
Fluconazole	Verapamil
CYP2D6 Inhibitors	
Celecoxib	Hydroxyzine
Chloroquine	Methadone
Chlorpheniramine	Moclobemide
Clemastine	Paroxetine
Clomipramine	Pyrilamine
Diphenhydramine	Quinidine
Fluoxetine	Terbinafine
Halofantrine	Tripeleminamine

Protocol 031-201-00301

Table 4.1-1 Example List of CYP3A4 and CYP2D6 Inhibitors and CYP3A4 Inducers Prohibited During the Trial	
CYP3A4 Inducers	
Carbamazepine	Phenytoin
Dexamethasone	Primidone
Efavirenz	Rifampin
Nevirapine	St. John's wort
Phenobarbital	Troglitazone

Note: The above is not an exhaustive list and there may be additional CYP3A4 and CYP2D6 inhibitors and CYP3A4 inducers that are prohibited during the trial.

4.2 Restricted Medications

Use and washout of any other therapy (prescription medication, over-the-counter, herbal medication, or vitamins) not listed in [Section 4.1](#) must be approved by the sponsor and the medical monitor.

Benzodiazepine use is allowed up to a maximum of 6 mg/day lorazepam or equivalent, but not within 8 hours of any rating scales during the trial. The use of intramuscular lorazepam is also permitted for emergent agitation, but only if deemed absolutely necessary by the investigator. The following guide should be used to determine approximate lorazepam equivalents: 1 mg lorazepam; = 5 mg diazepam; = 15 mg oxazepam; = 15 mg clorazepate. Subjects must not be on more than one benzodiazepine beyond the screening visit.

If a subject is receiving 2 benzodiazepines at the screening visit (eg, lorazepam and oxazepam), attempts should be made to discontinue one of the benzodiazepines, if clinically warranted, to allow potential subjects to enter the trial. The second benzodiazepine should be tapered off over an appropriate amount of time within the 45-day screening period to prevent side effects, and the subject should be maintained on the remaining benzodiazepine for at least 14 days prior to the administration of Abilify MyCite. Benzodiazepine use is allowed during the trial to manage AEs such as agitation, anxiety, and insomnia; however, non-benzodiazepine sleep aids are recommended for insomnia. Combined use of both drug classes (ie, benzodiazepines and non-benzodiazepine sleep aids) as treatment for insomnia is not allowed. Benzodiazepine use should be discontinued as soon as the AE for which it was initiated subsides, as per the investigator's discretion to avoid any withdrawal effects.

Medications that are restricted during the trial are listed in [Table 4.2-1](#).

Protocol 031-201-00301

Table 4.2-1 Medications Restricted During the Trial		
Medication	Screening	Treatment Period
Anticholinergics ^a	≤ 4 mg/day benztropine or equivalent	≤ 4 mg/day benztropine or equivalent
Propranolol (for akathisia or tremor) ^{b, c}	Maximum 60 mg propranolol per day	Maximum 60 mg propranolol per day
Benzodiazepines ^b	-	No more than one benzodiazepine and not in combination with other sleep aid medication

^aAnticholinergics are not allowed within 12 hours of any rating scales during any phase of the trial.

^bIs not allowed within 8 hours of any rating scales during any phase of the trial.

^cSubjects receiving propranolol for heart disease may remain on stable, pretrial doses, as needed, throughout the trial, so long as the total dose does not exceed 60 mg/day.

5 Reporting of Adverse Events

The following describes the methods and timing for assessing, recording, and analyzing safety parameters, as well as the procedures for eliciting reports of and recording and reporting AEs and intercurrent illnesses and the type and duration of the follow-up of subjects after AEs.

5.1 Definitions

An AE is defined as any untoward medical occurrence in a subject or clinical trial subject administered a medicinal product and which does not necessarily have a causal relationship with this treatment. Adverse events would not include information recorded as psychiatric history at screening for pre-planned procedures for which the underlying condition was known and no worsening occurred. An adverse reaction is any untoward and unintended response to Abilify MyCite related to any dose administered.

A suspected adverse reaction is any AE for which there is a reasonable possibility that Abilify MyCite caused the AE. For the purpose of Investigational New Drug (IND) safety reporting, “reasonable possibility” means there is evidence to suggest a causal relationship between Abilify MyCite and the AE. Suspected adverse reaction implies a lesser degree of certainty about causality.

An SAE includes any event that results in any of the following outcomes:

- Death.
- Life-threatening; ie, the subject was, in the opinion of the investigator, at immediate risk of death from the event as it occurred. It does not include an event that, had it occurred in a more severe form, might have caused death.

Protocol 031-201-00301

- Persistent or significant incapacity/disability or substantial disruption of the ability to conduct normal life functions.
- Requires inpatient hospitalization or prolongs hospitalization.
 - Hospitalization itself should not be reported as an SAE; whenever possible the reason for the hospitalization should be reported.
 - Hospitalizations or prolonged hospitalizations for social admissions (ie, those required for reasons of convenience or other non-medical need) are not considered SAEs.
- Congenital anomaly/birth defect.
- Other medically significant events that, based upon appropriate medical judgment, may jeopardize the subject and may require medical or surgical intervention to prevent one of the outcomes listed above; eg, allergic bronchospasm requiring intensive treatment in an emergency room or home, blood dyscrasias or convulsions that do not result in hospitalization, or the development of drug dependency or drug abuse.

A device-related SAE includes any event that results in any of the following outcomes:

- An event that reasonably suggests that a device has or may have caused or contributed to a death or serious injury.
 - Contributed to is defined as a death or serious injury that was or may have been attributed to a medical device, or that a medical device was or may have been a factor in a death or serious injury, including events occurring as a result of any of the following:
 - Failure.
 - Malfunction.
 - Improper or inadequate design.
 - Manufacture.
 - Labeling.
 - User error.
- Serious injury means an injury or illness that includes any of the following:
 - Is life-threatening.
 - Results in permanent impairment of a body function or permanent damage to a body structure.
 - Necessitates medical or surgical intervention to preclude permanent impairment of a body function or permanent damage to a body structure. Permanent means irreversible impairment or damage to a body structure or function, excluding trivial impairment or damage.
- Any of the following events that manufacturers or importers become aware of that reasonably suggests that one of their marketed devices:

Protocol 031-201-00301

- May have caused or contributed to a death or serious injury.
- Has malfunctioned and that the device or a similar device marketed by the manufacturer or importer would be likely to cause or contribute to a death or serious injury if the malfunction were to recur.

For the purpose of this trial, device-related SAEs include any event that is related to the IEM, patch, or the phone and app (reported to Otsuka).

If an AE is related to the patch, then the skin irritation scoring system will be completed by the investigator. Patch-related AEs Grade 2 or above will be considered medically significant for purposes of this trial.

Nonserious AEs are all AEs that do not meet the criteria for a "serious" AE.

Device-related nonserious AEs are considered skin reactions caused by patch graded lower than Grade 2.

Immediately Reportable Event (IRE):

- Any SAE.
- Any AE related to occupational exposure.
- Any nonserious AE related to the Abilify MyCite Patch.
- Potential serious hepatotoxicity (see [Section 5.4](#)).
- Pregnancies are also defined as IREs. Although normal pregnancy is not an AE, it will mandate Abilify MyCite discontinuation and must be reported on an IRE form to the sponsor. Pregnancy will only be documented on the AE eCRF if there is an abnormality or complication.

Severity: AEs will be graded on a 3-point scale and reported as indicated on the eCRF.

The intensity of an adverse experience is defined as follows:

- 1 = Mild:** Discomfort noticed, but no disruption to daily activity.
- 2 = Moderate:** Discomfort sufficient to reduce or affect normal daily activity.
- 3 = Severe:** Inability to work or perform normal daily activity.

Causality: Assessment of causal relationship of an AE to the use of Abilify MyCite is defined as follows:

- Related:** There is a reasonable possibility of a temporal and causal relationship between Abilify MyCite and the AE.

Protocol 031-201-00301

Not Related: There is no temporal or causal relationship between Abilify MyCite and the AE.

